### 1.2. Study Title

Phase IB Clinical trial of palbociclib and binimetinib in advanced triple negative breast cancer with hyperactivation of ERK and/or CDK4/6

### 1.3. Protocol code

PALBOBIN

[figure not shown]
[figure not shown]
## 1.4. Ethics Committee

CEIm Hospital 12 de Octubre

## 1.6. Investigational product

## Palbociclib and binimetinib

## 1.7. Phase

## Phase IB

## 1.8. Trial objectives

### Primary objective:

Primary objective of this study is to determine the 3-months PFS of palbociclib plus binimetinib in advanced triple negative breast cancer (TNBC), in patients with activation of ERK and/or CDK4/6.

### Secondary objectives:

- To determine response rate of the combination in advanced TNBC, in patients with activation of ERK and/or CDK4/6.
- CCI  
[REDACTED]
- To assess the safety of the combination in patients with advanced TNBC.

[figure not shown]
### Exploratory objective:

- CCI

## 1.9. Study design

This is an interventional, prospective, multicentric, single-arm, open label, phase IB clinical trial.

The following scheme depicts the basic trial design.

Patients diagnosed of metastatic or locally advanced non-curable TNBC that have received one or two treatment regimens for advanced disease will be candidates for the trial. A fresh tumor sample will be obtained in order to determine the phosphoproteomic profile of the tumor, preferably obtained after last treatment or the most recent sample as possible (from metastasis or first diagnosis according to sample availability) prior to study inclusion. If the patient has not a tumor sample available prior to study inclusion, the patient will not be allowed to participate in the study. Activation of the two kinases of interest will be determined centrally at CNIO. Only patients with scores above the upper quartile of at least one of them will be candidates. It is expected that approximately 40% of patients are positive for CDK4/6 and/or ERK.

Patients will then start treatment with continuous oral binimetinib and palbociclib 21 days on / 7days off, until disease progression. Tumor evaluation will be performed every 8 weeks. Study treatment will continue until disease progression, unacceptable toxicity, intercurrent serious disease, consent withdrawal or investigator's decision.

The study will be conducted at 8 Spanish sites and will enroll 25 patients.

## 1.10. Disease

Advanced triple negative breast cancer.

## **1.11. Study outcome measures**

### Primary outcome measure:

- Three-months PFS.

### Secondary outcome measures:

- Overall response rate.
- CCI  
[REDACTED]
- Number of patients experiencing each AE will be summarized by CTCAE grade to evaluate safety profile, according to NCI-CTC v 5 criteria.

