#### **5.1.3.5.1.2. Clinical Study CMEK162X1101**

Clinical Study CMEK162X1101 is an ongoing Phase 1, open-label, dose-escalation study of binimetinib as a single agent in Japanese patients with advanced solid tumors with an expansion cohort in patients with RAS or BRAF mutation.

Enrollment is complete, with 21 patients enrolled and treated with at least 1 dose of binimetinib (6 patients at 30 mg BID and 15 patients at 45 mg BID), including 14 patients in the dose-escalation phase and 7 patients in the dose-expansion phase.

Fourteen patients with advanced solid tumors received binimatinib in the dose- escalation phase and 11 were eligible for the dose-determining set. Two dose levels were evaluated (30 mg BID and 45 mg BID) and dose escalation was guided by an adaptive Bayesian Logistic Regression Model and implemented with the Escalation with Overdose Control principle. 45 mg BID was declared the MTD.

Following determination of the MTD in the dose-escalation phase, 7 patients were enrolled in the expansion phase and received binimatinib at the MTD (45 mg BID). No DLTs were reported in the expansion portion of the study.

All 21 patients (100%) reported at least 1 AE, the most common ( $\geq 20.0\%$  of patients) of which were blood CK increased (81.0%); AST increased (71.4%); retinal detachment (61.9%); diarrhea and lipase increased (57.1% each); ALT increased (52.4%); pyrexia, blood ALP increased, hypoalbuminemia, and dermatitis acneiform (47.6% each); amylase increased and dry skin (42.9% each); stomatitis, paronychia and rash (38.1% each); fatigue, edema peripheral and decreased appetite (33.3% each); cheilitis, GGT increased and hemoglobin decreased (28.6% each); and lymphopenia, constipation, blood creatinine increased, epistaxis and pruritus (23.8% each).

Seventeen patients (81.0%) experienced at least 1 Grade 3/4 AE; those reported for  $> 1$  patient were blood CK increased (7 patients [33.3%]); lipase increased and lymphopenia (4 patients [19.0%] each); and ALT increased, AST increased, cancer pain, fatigue, GGT increased and pneumonia (2 patients [9.5%] each). All other Grade 3/4 AEs occurred in 1 patient (4.8%) each.

Ten patients (47.6%) reported at least 1 SAE on study or within 28 days of the last dose of binimatinib. Serious AEs reported in  $> 1$  patient was pneumonia (2 patients [9.5%]). All other SAEs occurred in 1 patient (4.8%) each.

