#### **5.1.3.5.1.3. Clinical Study CMEK162X2201**

Clinical Study CMEK162X2201 is an ongoing Phase 2, open-label study of single- agent binimatinib in adult patients with locally advanced and unresectable or metastatic malignant cutaneous melanoma with BRAF V600 or NRAS mutation.

Enrollment is complete, with 183 patients enrolled and treated with at least 1 dose of binimatinib (158 patients at 45 mg BID [41 BRAF mutant and 117 NRAS mutant] and 25 patients at 60 mg BID [all BRAF mutant]). This section describes the data for the 25 patients treated with binimatinib 60 mg BID [all BRAF mutant]) as of the data cutoff date for the primary analysis (07 January 2014).

As of the data cutoff date for the primary analysis (07 January 2014) 25 patients were treated with binimatinib 60 mg BID. All 25 patients (100%) reported at least 1 AE, the most common ( $\geq 20.0\%$  of patients) of which were blood CK increased and edema peripheral (56.0% each); diarrhea (52.0%); fatigue and nausea (48.0%

each); retinopathy (40.0%); vomiting (36.0%); dermatitis acneiform (32.0%); arthralgia (24.0%); and dry skin, hypertension and rash (20.0% each).

Eighteen patients (72.0%) in the 60 mg BID cohort experienced at least 1 Grade 3/4 AE; those reported for > 1 patient were blood CK increased (6 patients [24.0%]); nausea and vomiting (3 patients [12.0%] each); and AST increased, blood ALP increased, blood lactate dehydrogenase increased, gastritis and syncope (2 patients [8.0%] each). All other Grade 3/4 AEs occurred in 1 patient (4.0%) each.

Nine patients (36.0%) in the 60 mg BID cohort reported at least 1 SAE on study or within 30 days of the last dose of binimetinib. Serious AEs reported in > 1 patient was gastritis (2 patients [8.0%]). All other SAEs occurred in 1 patient (4.0%) each.

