## 6.3. Secondary endpoints

- Overall response rate.
- CCI [REDACTED]
- Number of patients experiencing each AE will be summarized by CTCAE grade to evaluate safety profile, according to NCI-CTC v 5 criteria.

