#### **Ocular AESIs**

Retinopathy excluding RVO events were the most common AESI grouping reported. Retinopathy excluding RVO events reported in  $> 5.0\%$  of patients were vision blurred, retinopathy, subretinal fluid, retinal detachment, visual field defect and macular edema. Events in the RVO grouping were uncommon.

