#### **12.5.2. Secondary Safety evaluations**

AEs and toxicity will be evaluated according NCI CTCAE vs 5.0 criteria. AEs and toxicities will be presented by frequency distribution and percentage according to CTCAE grade.

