## 9. SAFETY ASSESSMENT

### 9.1. Safety Assessment; general considerations

The assessment will be performed for safety population defined in [section 5.1](#). Adverse events will be evaluated according to NCI CTCAE vs 5 criteria. Adverse events will be coded by the latest available version of MedDRA dictionary. AEs will be evaluated with the MedDRA code by system organ class (SOC) and preferred term (PT).

The analysis will be performed with the information completed into the adverse event eCRF section.

The analysis of adverse events will be performed per patient, for that the maximum grade for each adverse event completed of each patient will be calculated.

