### 9.2. Adverse Events

All adverse events evaluated will be described. The analysis of AEs will be described the following:

- The number and percentage of patients with at least one adverse event.
- The number and percentage of patients with each adverse event by grades (1-5).

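### No planned safety table counts patients with a toxicity that is coded under several terms, and SAP 9.5 (AESI) repeats the SAE analysis instead of filling the gap

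*Protocol*

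**What the plan says.** Protocol 1.11 and 6.3 give the same safety endpoint: "Number of patients experiencing each AE will be summarized by CTCAE grade to evaluate safety profile". Protocol 12.5.2 adds only that "AEs and toxicities will be presented by frequency distribution and percentage according to CTCAE grade".

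SAP 9.1 sets the level of counting: "AEs will be evaluated with the MedDRA code by system organ class (SOC) and preferred term (PT". It takes each patient's maximum grade within each adverse event. SAP 9.2 then plans a count of patients with any adverse event, and "The number and percentage of patients with each adverse event by grades (1-5". SAP 9.3 and 9.4 use the same layout for related and for serious events.

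SAP 9.5 carries the AESI heading. Its listing is introduced as one of serious adverse events, and both of its counts are of patients with serious adverse events. It defines no AESI category. SAP 9.4 holds only a yes/no AESI flag in the SAE listing.

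Protocol 11.3.6, by contrast, describes earlier binimetinib safety by AESI groupings, among them retinopathy excluding retinal vein occlusion (RVO), rash, muscle enzyme changes, liver tests, oedema and hypertension. Neither document carries these groupings into the planned analysis.

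**The concern.** A table with one row per preferred term answers the question of how many patients had that term. It does not answer how many had a toxicity that investigators and coders may record under two or more terms. Adding the rows counts some patients twice; taking the largest row can miss patients. The maximum-grade rule has the same limit, because a patient with Grade 2 under one term and Grade 3 under a related term appears in two rows at two grades.

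Safety of the combination is a secondary objective of a 25-patient trial. The reference data in Protocol 11.3.6 are given per grouping (for example liver test abnormalities 20-26% and left ventricular dysfunction 6-8%), so term-level rows from this trial cannot be set against them like for like. If grouping is left until the results are known, the choice of terms can be influenced by what they show.

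**Working it through.** The plan states no figure that this point depends on, so there is nothing to reproduce. The check has two parts.

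**1. Is there a grouping rule anywhere?**

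- Protocol 1.11, 6.3 and 12.5.2: each AE, by grade. No grouping.
- SAP 9.1 to 9.4: system organ class and preferred term. No grouped terms or MedDRA query. The word toxicity in SAP 9.3 means an AE related to study treatment, not a group.
- SAP 9.5: AESI heading, SAE content.
- Protocol 11.3.6: groupings, used only to describe earlier data. Its dermatologic part alone separates rash, skin infections, nail disorders and severe cutaneous reactions. The SAP links no system organ class to any of these groupings.

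**2. How much does a split leave open?**

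If *a* of *n* patients have one term and *b* have the other, the number with at least one lies between max(*a*, *b*), when overlap is complete, and min(*n*, *a* + *b*), when there is none.

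*Rash, Clinical Study CMEK162X1101 (Protocol 5.1.3.5.1.2, n = 21).* Dermatitis acneiform is reported at 47.6%, and the list continues with "stomatitis, paronychia and rash (38.1% each".
- 0.476 × 21 = 10 patients; 0.381 × 21 = 8 patients.
- Lower bound: 10/21 = 47.6%.
- Upper bound: (10 + 8)/21 = 18/21 = 85.7%.
- If the two terms were independent: 1 − (11/21)(13/21) = 67.6%.

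*Rash, Clinical Study CMEK162X2201, 60 mg BID cohort (Protocol 5.1.3.5.1.3, n = 25).* The list includes "dermatitis acneiform (32.0%); arthralgia (24.0%); and dry skin, hypertension and rash (20.0% each".
- 0.32 × 25 = 8 patients; 0.20 × 25 = 5 patients.
- Lower bound: 8/25 = 32%.
- Upper bound: (8 + 5)/25 = 13/25 = 52%.

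*Rash at Grade 3, Clinical Study ARRAY-162-111 (Protocol 5.1.3.5.1.1, n = 93).* Dermatitis acneiform and rash are listed with 2 patients each.
- Lower bound: 2/93 = 2.2%.
- Upper bound: 4/93 = 4.3%.

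*Retinal events (Protocol 11.3.6, Ocular AESIs).* One grouping, retinopathy excluding RVO, contains at least these terms, each in more than 5% of patients: "vision blurred, retinopathy, subretinal fluid, retinal detachment, visual field defect and macular edema". The section calls it the most common AESI grouping and lists it among those reached by at least 20% of patients in one or other population. Individual term rates are not given, so no range can be calculated.

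*Illustration for this trial (assumption: 10 of 25 patients have one toxicity, coded evenly under two terms without overlap).* The patient-level rate is 10/25 = 40% (exact 95% CI 21-61%). The planned table would show two rows of 5/25 = 20% (exact 95% CI 7-41%).

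**The case against.** Counting each patient once per term at her maximum grade, by system organ class and preferred term, is a complete descriptive plan and agrees with the protocol. That stands: there is no contradiction with the endpoint, and those tables should stay.

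A reader might infer that the grouped rate would be lost. The documents do not support that. SAP section 4 puts all available safety data into listings and tabulations, so with 25 patients anyone holding the patient-level data can count who had either term. What is missing is a rule fixed in advance and a table that applies it.

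A reader might also extend the point to every toxicity. The documents do not support that either:
- Protocol 11.3.6 states that every patient in the muscle enzyme grouping had an event under blood CK increased, so one row already gives that rate. Peripheral oedema and hypertension are also dominated by one term.
- Anemia and hemoglobin decreased appear in different studies (ARRAY-162-111 and CMEK162X1101), so no split within one study is shown. For neutrophils the protocol speaks only of neutropenia.

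Protocol 11.3.1 asks for recording by CTCAE v5.0 and for the main diagnosis when signs belong to one disease. Both lessen splitting at source, but neither merges related terms. Treating rash and dermatitis acneiform as one toxicity is a clinical judgement. Protocol 5.1.3.6 names the two together among skin toxicities but leaves the exact group to be defined, which is a reason to write it down beforehand.

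**Conclusion.** The point holds for toxicities recorded under several terms. The documents show this for rash and retinal events. For rash, term-level rows leave 38.1 percentage points open in one earlier study (47.6% to 85.7%) and 20 points in another (32% to 52%). The upper ends need zero overlap between the terms, and the loss in this trial would be small if coding proved uniform.

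A reader might infer that splitting hides a large part of the severe toxicity. The documents do not show that: the only Grade 3 figures that give both skin terms leave a range of 2.2% to 4.3%. Nor do the documents set an AE rate on which a decision about the combination turns, so the consequence is for description and for comparison with earlier data. That comparison has its own limit, because Protocol 11.3.6 does not identify the populations behind its percentages.

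SAP 9.5 is a plain defect whatever the degree of splitting: the section meant for AESIs contains no AESI count.

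**What to change.** 1. Correct SAP 9.5 so that its listing and counts are of AESIs instead of repeating the SAE text.
2. Add one table by the AESI groupings in Protocol 11.3.6, with at least rash and retinopathy excluding RVO. List the preferred terms of each group in the SAP, which is in any case to be signed before database lock.
3. Count each patient once per group at her highest grade across the group's terms. Report the number, the percentage and the exact 95% CI for any grade and for Grade 3 or higher. Protocol 12.1 already allows a CI where it is considered relevant.
4. Keep the tables by system organ class and preferred term as they are.

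The cost is one term list, agreed with clinical input, and one extra table from data already coded. It adds no visit, assessment or site work.

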### Exploratory outcome measures:

- CCI  
[REDACTED]  
[REDACTED]  
[REDACTED]

## **1.12. Study population and number of patients**

It is expected to include 25 patients in this trial.

Patients diagnosed of metastatic or locally advanced non-curable TNBC that have received one or two treatment regimens for advanced disease will be included in this study.

## **1.13. Selection criteria**

### **1.13.1. Inclusion criteria**

1. Women >18 years-old.
2. Diagnostic of metastatic or locally advanced non-resectable TNBC.
3. Patient must have received a minimum of one and a maximum of two treatment lines for metastatic TNBC. Previous treatments can be of any nature (chemotherapy, immunotherapy, antiangiogenics, experimental therapy, etc.).

Women with known BRCA1/BRCA2 germline mutations must have received a platinum based treatment or treatment with a PARP inhibitor.

4. Patient must have experienced disease progression to the previous treatment line according to the RECIST 1.1 or iRECIST criteria.
5. Availability of tumor tissue for ERK and CDK4/6 testing is mandatory prior to study inclusion, preferably obtained after last treatment or the most recent sample as possible (from metastatic site or first diagnosis according to sample availability). If the patient has not a tumor sample available prior to study inclusion, the patient will not be allowed to participate in the study.
6. Ability to understand and signing of the written patient information/informed consent form (PIS/ICF) for ERK and CDK4/6 testing. ERK and CDK4/6 testing will be performed centrally at CNIO.
7. Ability to understand and signing the written PIS/ICF for study treatment eligibility. Signed informed consent form must be available before any study- specific procedure for the respective study parts may begin.
8. Positivity for ERK and/or CDK4/6, defined as showing an H-score above the top-quartile according to published definitions [1].
9. ECOG performance status of 0-1.
10. Evaluable disease according to RECIST 1.1 criteria.
11. Life expectancy >24 weeks.
12. Adequate bone marrow, liver and renal function as assessed by laboratory requirements conducted within 7 days before first study drug administration:
  - a. Absolute neutrophil count (ANC)  $\geq 1.500/\text{mm}^3$  (without granulocyte colony-stimulating factor support within 2 weeks before the first study drug administration)
  - b. Hemoglobin  $\geq 9 \text{ g/dL}$  (without transfusion or erythropoietin within 4 weeks before the first study drug administration)
  - c. Platelet count  $\geq 100.000/\text{mm}^3$  (without transfusion within 2 weeks before the first study drug administration)
  - d. Total bilirubin  $\leq 2 \times$  the upper limit of normal (ULN).

**CONFIDENTIAL**

- e. Alanine aminotransferase (ALT) and aspartate aminotransferase (AST)  $\leq 2.5 \times \text{ULN}$  ( $\leq 5$  times ULN for patients with liver metastases)
- f. Glomerular filtration rate (GFR)  $> 50 \text{ mL/min}/1.73 \text{ m}^2$  according to the modification of diet in renal disease (MDRD) abbreviated formula.

13. Patients must have recovered to  $\leq$  Grade 1 in terms of toxicity from prior treatments (excluding neuropathy which can be  $\leq$  Grade 2, and alopecia).

14. Patients must be able to take oral medications.

15. Patients must have adequate cardiac function, defined as:

- a. Left ventricular ejection fraction (LVEF)  $> 50\%$  as determined by echocardiogram or multigated acquisition scan (MUGA).
- b. QTc  $< 480$  msec.

16. Negative serum pregnancy test in women of childbearing potential (performed within 7 days before the first treatment). Negative results must be available before the first study drug administration.

A postmenopausal state is defined as no menses for 12 months without an alternative medical cause. A high follicle stimulating hormone (FSH) level in the postmenopausal range may be used to confirm a post-menopausal state in women not using hormonal contraception or hormonal replacement therapy. However in the absence of 12 months of amenorrhea, a single FSH measurement is insufficient.

Pregnancy test will not be performed in postmenopausal women.

17. Women of reproductive potential must agree to use adequate contraception when sexually active. This applies for the time period since the signature of the informed consent form and until at least 1 month after the last study drug administration. The definition of adequate contraception will be based on the judgment of the investigator and on local requirements. Acceptable methods of contraception include, but are not limited to, (i) condoms (male or female)

with or without a spermicidal agent; (ii) diaphragm or cervical cap with spermicide; (iii) intra-uterine device; (iv) hormone-based contraception.

Zoledronic acid or denosumab started prior to trial registration is allowed, but in case they are required after initiation of trial procedures, adequate justification is required.

### **1.13.2. Exclusion criteria**

1. Participants who have had chemotherapy, radiotherapy, or major surgery within 2 weeks (6 weeks for nitrosoureas or mitomycin C) prior to entering the study.
2. Patients that received during the metastatic disease setting any of the study drugs, palbociclib or binimatinib.
3. Participants receiving any other study agents concurrently with the study drugs. Zoledronic acid or denosumab for bone metastases, started at least 15 days prior to enrollment are allowed.
4. Participants with symptomatic brain metastases that require chronic steroids. Patients with a history of brain metastases are permitted to enroll as long as they have been treated, are off of steroids, and have been stable for a minimum of one month on imaging.
5. Irradiation of single lesions in the last 28 days prior to trial recruitment, if it is the only location of the disease and it has not progressed. Patients with radiated single lesions that has progressed are allowed.
6. Concurrent use of strong CYP3A4 inhibitors/inducers is prohibited due to drug-drug interactions with palbociclib. Moderate CYP3A4 inhibitors/inducers should be used with caution.
7. Uncontrolled intercurrent illness including, but not limited to:
  - a. ongoing or active infection requiring systemic treatment
  - b. symptomatic congestive heart failure
  - c. cardiac arrhythmia

- d. psychiatric illness/social situations that would limit compliance with study requirements
- e. hypertension, defined as systolic blood pressure > 160 mmHg despite medical management
- f. myocardial infarction, unstable angina, coronary artery bypass grafting, coronary angioplasty, or stenting < 6 months prior to screening

8. History of QT syndrome, Brugada syndrome, known history of QTc prolongation, or Torsades de Pointes.
9. History of Gilbert's syndrome.
10. History of neuromuscular disorders that are associated with elevated CK (e.g. inflammatory myopathies, muscular dystrophy, amyotrophic lateral sclerosis, spinal muscular atrophy).
11. Previous or concurrent cancer except:
  - a. cervical carcinoma in situ
  - b. treated basal-cell carcinoma or squamous cell skin cancer
  - c. any other cancer curatively treated > 3 years before the first study drug administration
12. Malabsorption syndrome or uncontrolled nausea, vomiting, or diarrhea that may interfere with the absorption of oral study medication in the opinion of the investigator.
13. Pregnant women or breast-feeding.
14. Known HIV-positive individuals on combination antiretroviral therapy.
15. Active hepatitis B virus (HBV; chronic or acute; defined as having a known positive hepatitis B surface antigen [HBsAg] test at the time of screening) or hepatitis C infection requiring treatment.

- a. Patients with past HBV infection or resolved HBV infection (defined as the presence of hepatitis B core antibody [HBcAb] and absence of HBsAg) are eligible if HBV DNA is negative.
- b. Patients positive for hepatitis C virus (HCV) antibody are eligible only if polymerase chain reaction is negative for HCV RNA.

16. Any condition that in the opinion of the investigator would interfere with evaluation of study treatment or interpretation of patient safety or study results, or inability to comply with the study and follow-up procedures.

17. Participation in another clinical study with investigational medicinal products within 4 weeks before the first study drug administration.

18. Clinically active infections within 2 weeks before the first study drug administration.

19. Treatment with therapeutic oral or i.v. antibiotics within 2 weeks before the first study drug administration. Patients receiving prophylactic antibiotics (e.g. for prevention of a urinary tract infection or to prevent chronic obstructive pulmonary disease exacerbation) are eligible.

20. Known hypersensitivity to any of the study drugs, study drug classes, or excipients in the formulation.

21. Current diagnosis of any retinal disorders including retinal detachment, retinal pigment epithelial detachment (RPED), serous retinopathy or retinal vein occlusion or risk factors for RVO (e.g., uncontrolled glaucoma or history of hyperviscosity or hypercoagulability syndrome).

22. Peripheral sensory neuropathy of CTCAE v.5.0 Grade 2 or higher

23. Major surgery, open biopsy or significant traumatic injury within 4 weeks before the first study drug administration (central line surgery is not considered major surgery).

24. Renal failure requiring peritoneal dialysis or hemodialysis.

25. Substance abuse, medical, psychological or social conditions that may interfere with the patient's participation in the study or evaluation of the study results.

